9.2 SL-172154 Concentration Measures

SL-172154 concentration values will be sorted by dose level, dosing schedule, sample collection day, and nominal time points in the listing. All SL-172154 concentration values including BLQ will be listed in the same precision as the source data.

SL-172154 concentration will be summarized by dose level for each nominal time point relative to the EOI. Standard summary statistics will be calculated (i.e., mean, standard deviation [SD], median, minimum, maximum, coefficient of variation (CV%), geometric mean, geometric CV%).

Individual subject concentration-time profiles and median/mean profiles by dose level will be plotted for C1D1, C1D15 and C2D1, using the actual time from SOI for individual plots and the nominal time from EOI for medina/mean profiles. Each of the figures will contain one plot on the untransformed scale (i.e. linear plot) and one plot on the log transformed scale (i.e. semi-log plot). For mean concentration profile plot, mean+/- SD for each dose level will be plotted. For median concentration profile plot, median along with minimum and maximum for each dose level will be plotted. Individual subject concentration-time profiles using actual time from SOI (semi-log plot) will also be plotted along with infusion actual start and end time (including any interruptions) for each dose level at C1D1, C1D15 and C2D1.

Dose normalized concentration will be calculated by dividing total administered dose (mg). Mean (SD) dose normalized concentration time profile will be plotted for each dose level at C1D1, C1D15 and C2D1.

9.3 PK Parameters

The PK parameters will be derived from the concentration-time data using the actual collection time from SOI. The PK parameters will be calculated by standard non-compartmental analysis (NCA) as data permits. At least one post-dose concentration is required for C_{max} calculation, and at least three consecutive post-dose concentrations are required for AUC parameter calculation.

Table 6 SL-172154 PK Parameters

C _{max}	Maximum observed concentration over a dosing interval
C_{trough}	Observed concentration at the end of a dosing interval.
T _{max}	Time of maximum observed concentration
AUC _{0-last}	The area under the serum concentration time curve, from time 0 to the last
	quantifiable concentration, calculated by a combination of linear and
	logarithmic trapezoidal methods (Linear up/log down method).
AUC_{0-inf}	Area under the serum concentration time curve from time 0 extrapolated to
	infinity, calculated as AUC _{last} + C _{last} /terminal elimination rate constant (λz).
	Reliability of AUC _{0-inf} values is contingent on the percent of the total area
	obtained by extrapolation: AUC _{0-inf} values with <20% of the total area
	coming from Clast/λz are considered acceptable. Any exceptions to the above
	procedures will be clearly documented/justified in the PK report.

AUC _{tau}	The area under the serum concentration time curve over the dosing interval, calculated by a combination of linear and logarithmic trapezoidal methods (Linear up/log down method).
%AUCext	Percentage of AUCo-inf due to extrapolation from Tlast to infinity
t _{1/2}	Terminal elimination half-life, estimated using the equation $[\ln(2)/\lambda_z]$
CL	Clearance; calculated as Dose/AUC _{0-inf} for C1D1 and Dose/AUC _{tau} for later time unless specified otherwise
Vz	Volume of distribution, calculated as Dose/ $(\lambda_z * \text{AUC0-inf})$ for C1D1 and Dose/ $(\lambda_z * \text{AUC}_{tau})$ for later time unless specified otherwise
AR _{AUCtau}	Accumulation ratio of AUC _{tau} (C1D15/C1D1 and C2D1/C1D1).
AR _{Cmax}	Accumulation ratio of C _{max} (C1D15/C1D1and C2D1/C1D1).

The elimination rate constant (λ_z) will be determined if the log-linear terminal elimination phase is apparent and excludes C_{max} . The λ_z will only be considered reliable if the adjusted coefficient of determination (adj-R²) is greater than or equal to 0.8. Parameters dependent on λ_z (i.e., $t_{1/2}$, AUC_{0-inf}, AUC_{%ext}, CL, Vz) will not be presented if λ_z cannot be estimated.

The following PK parameters will be calculated for diagnostic purposes and listed but not be summarized:

- λ_z lower: Lower limit of time (h) included in the calculation of λ_z
- λ_z N: Number of data points used in the calculation of λ_z
- λ_z upper: Upper limit of time (h) included in the calculation of λ_z
- Adjusted-R²: Regression coefficient for calculation of λz

All PK parameters will be sorted by dose level/schedule in the listing and summarized by dose level for each PK sample collection day. For each of the PK parameters, except T_{max} , the following summary statistics will be calculated: median, minimum, maximum, arithmetic mean, standard deviation, CV%, geometric mean, and geometric CV%. For T_{max} , median, minimum, and maximum will be calculated. All PK parameters will be reported with the same precision as the source concentration data except that T_{max} and $t_{1/2}$ will be reported with 2 decimal places and λ_z will be reported with at least 3 significant figures.

Box plots of AUC_{0-inf}, AUC_{0-last}, AUC_{tau}, C_{max}, and C_{trough} for each dose level will be produced for C1D1, C1D15 and C2D1 as data permit.

To graphically examine the accumulation over time, box plots of C_{max} and AUC_{0-last} as a function of time (in day) will be produced for each dose level. Mean C_{trough} with SD will be presented on linear scale as a function time (in day) for each dose level.

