3.3 SL-172154 Dose Escalation Plan

Dose escalation will begin on Schedule 1 at the starting dose of 0.1 milligrams per kilogram (mg/kg) as outlined in Table 1 below. Intermediate or higher dose levels not shown may be explored based on emerging data (e.g., safety and pharmacodynamic data). Dose escalation of SL-172154 will not exceed half-log increments. The DLT assessment period is 28 days in length and ends 14 days after the last dose is administered in the first cycle on Schedule 1 and 7 days after the last dose is administered on Schedule 2. Dose escalation will follow the mTPI-2 decision rules outlined in Table 7 in Section 9.1.

- Schedule 1 administration for SL-172154: Given on days 1, 8, and 15 in cycle 1 over 28 days and then every two weeks thereafter on days 1 and day 15 in cycles \geq 2 every 28 days.
- Schedule 2 administration for SL-172154: Given on days 1, 8, 15 and 22 of each 28-day cycle
- Cycle length for Schedules 1 and 2: 28 days
- **DLT assessment period for Schedules 1 and 2**: 28 days

Table 1: SL-172154 Dose Escalation Plan in Phase 1
--

	Dose LevelIV Dose of SL-172154 (mg/kg) ^{a,b,c,d,e} Duration of Infusion ^d				
Lev	evel 1 - starting dose 0.1 30 minutes (+/- 10 minutes)				
Lev	vel 2	0.3	30 minutes (+/- 10 minutes)		
Lev	vel 3	1.0	30 minutes(+/- 10 minutes)		
Level 4 3.0 60 minutes (+/- 15 minutes)					
Level 5 10.0 60 minutes (+/- 15 minutes)					
a) b)	cycle 1 and then on days Dose escalation on Sched once weekly on days 1, 8	1 and 15 in cycles \geq 2. Jule 2 may be tested: If Schedule 2 is of , 15, and 22 of each 28-day cycle.	in 28-day cycles on days 1, 8, and 15 in pened, SL-172154 may be administered		
c) d)	kg. For subjects with body weight >100 kg, the dose to be administered should be the same as that calculated for a subject weighing 100 kg (see Section $5.1.4$).				
e)	Infusion time may change based on final drug volume needed for administration, safety and tolerability of the infusion for the subject and/or observed safety findings during the study. Please refer to the Study				

Pharmacy Manual (SPM) for details.

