9.2.6 Pharmacokinetic Analysis

The PK analysis will be based on the PK population. Serum concentrations for SL-172154 will be summarized using tabular and graphical format. SL-172154 PK parameters will be summarized and analyzed using appropriate statistical methods. The Pharmacokinetics of SL-172154 will be described using the PK parameters listed in Table 8, as data permit.

C _{max}	Maximum observed concentration
T _{max}	Time of maximum observed concentration
AUC _{0-last}	The area under the serum concentration time curve, from time 0 to the last quantifiable concentration, calculated by a combination of linear and logarithmic trapezoidal methods (Linear up/log down method).
AUC _{0-t}	The area under the serum concentration time curve, from time 0 to time=t, calculated by a combination of linear and logarithmic trapezoidal methods (Linear up/log down method).
AUC _{0-inf}	Area under the serum concentration time curve from time 0 extrapolated to infinity, calculated as $AUC_{last} + C_{last}$ /terminal elimination rate constant (λ_z). Reliability of AUC_{0-inf} values is contingent on the percent of the total area obtained by extrapolation: AUC_{0-inf} values with <20% of the total area coming from C_{last}/λ_z are considered acceptable. Any exceptions to the above procedures will be clearly documented/justified in the PK report.
AUC _{tau}	The area under the serum concentration time curve, over the dosing interval following doses > first dose, calculated by a combination of linear and logarithmic trapezoidal methods (Linear up/log down method).
%AUC _{ext}	Percentage of AUC _{0-inf} due to extrapolation from T _{last} to infinity
t _{1/2}	Terminal elimination half-life, estimated using the equation $[\ln(2)/\lambda_z]$
CL	Clearance; calculated as Dose/AUC _{0-inf}
Vz	Volume of distribution; calculated as Dose/($\lambda_z * AUC_{0-inf}$)

Table 8: Serum SL-172154 PK Parameters

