6.7 Study Drug Exposure

The individual subject SL-172154 administration including total dose administered, infusion concentration, infusion volume, rate of infusion, start and end time, duration of infusion, and infusion outcome for each infusion will be presented in a data listing.

Total number of doses received, duration of treatment, average dose received, and dose compliance will be summarized.

Subject average dose is calculated as the cumulative dose (mg) that a subject received divided by the total number of doses received.

Duration of SL-172154 treatment is defined as:

- Minimum of (date of death plus 1 day, data cutoff date plus 1 day, and date of last dose + 14 days if last dose is C1D15 or beyond or + 7 days if last dose is C1D1 or C1D8) minus date of first study drug administration for subjects in Schedule 1.
- Minimum of (date of death plus 1 day, data cutoff date plus 1 day, and date of last dose + 7 days) minus date of first study drug administration for subjects in Schedule 2.

In addition to mean, median, minimum and maximum, duration on treatment will also be summarized in the following categories: \leq 4 weeks, \geq 4 - 8 weeks, \geq 8 - 12 weeks, \geq 12 - 16 weeks, \geq 16 weeks.

Dose compliance is defined as the total mg of SL-172154 infused divided by the total mg of SL-172154 assigned, expressed as a percentage.

Duration of SL-172154 treatment will be plotted by subject using a horizontal bar graph with information regarding the time of first PR/CR and the first progressive disease (PD), dose level, best response (RECIST 1.1) and treatment discontinuation information for each subject.

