9. PHARMACOKINETIC ANALYSES

The merge of SL-172154 serum concentration with CRF data will be performed after database lock by Shattuck Labs to generate a dataset with actual PK sampling times, actual time relative to

the start of infusion, and SL-172154 concentrations. Derivation of PK parameters will be performed by using Phoenix WinNonlin (Version 8.2 or higher).

Unless otherwise specified, all PK data analysis will be based on the PK population and summarized by dose levels regardless of dosing schedules. Subjects who have infusion outcome as "Not Completed" on the PK sample collection day will be included in the summary of dose normalized concentration and PK parameter but will be excluded from other summary by dose level for the corresponding PK sample collection day.

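### SAP 9.3's two AUC accumulation measures compare unequal windows: the AUCtau ratio (14 d over 7 d on Schedule 1 as written) and the AUC0-last by-visit plots (24 h against 48 h)

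*SAP*

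**What the plan says.** SAP Section 9.3, Table 6, defines AUCtau as "The area under the serum concentration time curve over the dosing interval" and gives no numerical interval. Its accumulation ratio is "C1D15/C1D1 and C2D1/C1D1". Protocol Section 9.2.6, Table 8, limits AUCtau to the interval "over the dosing interval following doses > first dose" and also lists a partial area, "The area under the serum concentration time curve, from time 0 to time=t". SAP Table 6 drops that limit, needs a C1D1 AUCtau as denominator, and omits AUC0-t.

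Schedule 1 dosing is "Given on days 1, 8, and 15 in cycle 1 over 28 days and then every two weeks thereafter" (protocol Section 3.3). The treatment-duration rule in SAP Section 6.7 follows the same spacing: "14 days if last dose is C1D15 or beyond or + 7 days if last dose is C1D1 or C1D8". Schedule 2 is weekly throughout.

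SAP Section 9.3 also plans box plots of Cmax and AUC0-last by visit, introduced with "To graphically examine the accumulation over time" (Figures 14.3.7.10 and 14.3.7.11). Serial PK sampling runs to 48 h after end of infusion at C1D1 (protocol Table 2) and to 24 h at C1D15 and C2D1 (protocol Table 4). PK data are "summarized by dose levels regardless of dosing schedules" (SAP Section 9).

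**The concern.** An accumulation ratio should isolate the effect of repeated dosing, so numerator and denominator must cover the same length of time. If they do not, the ratio mixes accumulation with window length. Here the AUCtau ratio can be inflated on Schedule 1 because its numerator covers twice the time, and the AUC0-last plot can show a fall because later visits are sampled for half as long.

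Characterising PK after single and multiple doses is a secondary objective, and PK is among the data considered for the RP2D and for a move to the weekly schedule. A reader of these outputs could not tell a change in exposure from a change in window.

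**Working it through.** The plan states no accumulation figure, so there is nothing to reproduce. The check sets the windows side by side and then sizes the mismatch under an assumed model.

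**Dosing intervals.** Schedule 1 doses fall on study days 1, 8, 15, 29 and 43 (protocol Sections 3.3 and 6.1).
- Schedule 1: after C1D1, 8 − 1 = 7 d; after C1D15, 29 − 15 = 14 d; after C2D1, 43 − 29 = 14 d.
- Schedule 2: 8 − 1 = 7 d, 22 − 15 = 7 d, 36 − 29 = 7 d.

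Read as written, both AUCtau ratios are therefore 14 d over 7 d on Schedule 1 and 7 d over 7 d on Schedule 2.

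**Can the Schedule 1 AUCtau be observed?** The C1D8 predose sample (protocol Table 3) closes the C1D1 interval, and the C2D1 predose sample (Table 4) closes the C1D15 interval. Nothing closes the C2D1 interval, because Table 4 lists only cytokines at C2D15. That AUCtau needs extrapolation from 24 h to 14 d.

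**AUC0-last horizons.** On serial samples alone they are 48 h, 24 h and 24 h at C1D1, C1D15 and C2D1. The SAP does not say whether the next visit's predose sample belongs to the preceding profile. If it does, the Schedule 1 horizons are about 168 h, 336 h and 24 h, which still do not match.

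**Half-life inputs.** No human estimate is given. Monkey values are 0.4 h at 1 mg/kg and 1.1 and 0.9 h at 10 and 40 mg/kg (protocol Section 1.2.4). Inclusion criterion 10 expects 30 days to exceed 5 half-lives, which implies a ceiling of 30/5 = 6 d but is not an estimate. The quantification limit is 10 ng/mL (SAP Section 9.1).

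**Interval effect alone.** Assume linear one-compartment kinetics with half-life H in days. The 14 d over 7 d factor is (1 − 2^(−14/H)) / (1 − 2^(−7/H)) = 1 + 2^(−7/H).
- H = 1 d: 1 + 0.008 = 1.01
- H = 2 d: 1 + 0.088 = 1.09
- H = 3 d: 1 + 0.198 = 1.20
- H = 6 d (the ceiling): 1 + 0.445 = 1.45

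It passes 1.10 at H = 7 × ln 2 / ln 10 = 2.1 d, about 51 h.

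**Sampling effect alone.** With half-life h in hours and drug still quantifiable at 48 h, the 24 h over 48 h factor is 1 / (1 + 2^(−24/h)). The peak needed to be at the limit at 48 h is 10 × 2^(48/h).
- h = 6: 1/1.0625 = 0.94; peak 2,560 ng/mL
- h = 12: 1/1.25 = 0.80; peak 160 ng/mL
- h = 24: 1/1.5 = 0.67; peak 40 ng/mL

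The loss passes 10% at h = 24 × ln 2 / ln 9 = 7.6 h.

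**Monkey check.** A peak of 1,230 ng/mL with a 0.4 h half-life reaches 10 ng/mL after 0.4 × log2(123) = 2.8 h. A peak of 727,000 ng/mL (40 mg/kg, range-finding study) with the 0.9 h half-life from the GLP study does so after 0.9 × log2(72,700) = 14.5 h. Both profiles end before 24 h, and every factor above is 1.00.

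**The case against.** The 14 d over 7 d reading is inferred. SAP 6.7 defines treatment duration, not a PK tau, and an analyst could set one tau in the software. That is fair, but the SAP does not say so, and a pre-specified ratio should not rest on an unwritten choice.

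No effect appears at the only half-lives reported, and the linear model sits uneasily with the target-mediated and antibody-driven clearance that protocol Section 3.2 describes. Both points stand: the sizes are conditional illustrations. The sampling horizons may also change with emerging data, as the footnotes to protocol Tables 2 and 4 allow.

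Like-for-like information already exists. SAP 9.2 summarises concentrations by nominal time and plots profiles at C1D1, C1D15 and C2D1, so exposure to 24 h can be compared by eye. AR_Cmax does not depend on window length. This lowers the stakes but does not repair the two AUC measures.

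A reader might infer that the two outputs must point in opposite directions, the ratio too high and the plot too low. The documents do not support that. It requires predose samples to close the AUCtau intervals while the same samples are left out of AUC0-last. With them in both, the model at a 2-day half-life (r = 2^(−3.5) = 0.088) gives a C1D15/C1D1 value of (1 + r + r²)(1 + r) = 1.19 for both measures. If the 336 h value is below the limit, AUC0-last instead gives (1 + r + r²)(1 − 2^(−0.5)) / (1 − r) = 0.35. The direction depends on a convention that the SAP leaves open.

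A reader might also infer that any fall in the AUC0-last plot would be artefact. It could be real, given the clearance mechanisms above; the plot cannot separate the two.

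**Conclusion.** The point holds as a mismatch of windows in two of the SAP's accumulation outputs. The unequal intervals follow from the dosing days, and the unequal serial sampling is explicit. Under the assumed linear model, the AUC0-last window effect exceeds 10% from a half-life of about 7.6 h if drug is quantifiable to 48 h. The Schedule 1 AUCtau interval effect exceeds 10% only from about 51 h. At the monkey half-lives both vanish.

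Pooling of schedules adds to the problem only for AUCtau-based ratios with different tau, and only at dose levels given on both schedules; Schedule 2 is optional. Splitting other PK summaries by schedule is a trade-off against very small cells, and recording the pooling in SAP Section 11 is bookkeeping.

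The change is worth making because a better measure is available from samples already collected and does not depend on knowing the half-life in advance. It does not touch dose escalation, since no escalation rule uses these outputs.

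**What to change.** - Base the AUC accumulation ratio and the by-visit AUC plots on AUC0-24h at C1D1, C1D15 and C2D1. Protocol Table 8 already provides for AUC0-t.
- State tau for each visit and schedule, and state whether the next visit's predose sample enters a profile.
- If AR_AUCtau is kept, use the same tau in numerator and denominator.
- Where a dose level is given on both schedules, do not pool AUCtau-based ratios that use different tau.

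The cost is SAP wording and one partial-AUC parameter, with no new sample or visit. The 24 h sample is timed from end of infusion with a ±2 h window, so some profiles need interpolation or a short extrapolation to reach 24 h from start of infusion. The most this can be is 24 h − (22 h + 20 min for the shortest permitted infusion) = about 1.7 h.

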9.4 Assessment of Dose Proportionality

An assessment of dose proportionality will not be based strictly on statistical rule criteria but rather, several factors will be considered when assessing dose proportionality, such as results derived from a Power Model (e.g., the slope estimate, and the width of the 95% confidence intervals), graphical evaluation (box plots of dose-normalized PK parameters) and descriptive statistics of PK parameters by dose, as data permit.

Dose normalized PK parameters will be calculated by dividing total administered dose (mg) for AUC_{0-inf}, AUC_{0-last}, AUC_{tau}, C_{max}, and C_{trough}. Additional dose normalized PK parameters may be calculated, if appropriate and as data permit. Dose proportionality will be evaluated graphically using box plots of dose normalized PK parameters (AUC_{0-inf}, AUC_{0-last}, AUC_{tau}, C_{max}, and C_{trough}) by dose level for C1D1, C1D15 and C2D1.

Dose proportionality will also be evaluated for the AUC_{0-inf}, AUC_{0-last}, AUC_{tau}, C_{max}, and C_{trough} using the power model as data permit. A statistical linear relationship between the ln-transformed PK parameters and the ln-transformed actual dose received in mg will be fitted by using a mixed effect model with ln-transformed dose as a fixed effect and subject as random effect. Additional predictors may be included in the model. The general form of the power mode is described as:

$$Ln(Y) = \beta_0 + \beta Ln (Dose) + \varepsilon$$

where Y represents the pharmacokinetic parameter. Note that $\beta = 1$ would correspond to perfect dose proportionality.

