In the GLP study, the occurrence of dose-dependent infusion-related reactions (IRRs) at 10 and 40 mg/kg (Days 15 or 22) resulted in early termination of dosing in these two dose groups with 2 monkeys in the 40 mg/kg group euthanized in extremis [a female on Day 15 (Dose 3) and a male on Day 22 (Dose 4)]. Minimally to moderately decreased platelets occurred at ≥10 mg/kg (Days 16 and 23) and transient, mild decreases in lymphocytes were seen in the 40 mg/kg group (both sexes on Days 2 and 16; 2 of 4 males on Day 23). Dose-dependent increases in splenic weight and increased lymphoid cellularity in the spleen and lymph node were noted and attributed to SL-172154 administration. These findings were reversed after a 4-week recovery period. Assessment of pharmacodynamic biomarkers showed that SL-172154 occupied CD40 and CD47 receptors on circulating blood cells and caused elevations in a number of serum cytokines. Transient and reversible complement activation was coincident with the production of ADA to SL-172154. Additionally, the presence of ADA from at least Day 15 (Dose 3) onward likely contributed to low or non-quantifiable plasma SL-172154 concentrations on Day 29. At the 1.0 mg/kg dose level, there were no clinical observations, abnormalities in clinical pathology parameters, or non-reversible pathology findings, thus 1.0 mg/kg was considered to be the no-observed-adverseeffect level (NOAEL) for intravenous infusion doses of SL-172154. The 1.0 mg/kg dose corresponded with mean Cmax and AUC_{0-last} values of 1230 ng/mL and 518 ng*h/mL on Day 1. The mean terminal elimination half-life $(t^{1/2})$ on Day 1 was approximately 0.4 hours following a 1 mg/kg dose and was higher with mean values of approximately 1.1 and 0.9 hours for the 10 mg/kg and 40 mg/kg dose groups, respectively.

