Schedule 1 will be evaluated first. A transition to Schedule 2 may be implemented if pharmacodynamic effects are not present or detectable in Schedule 1, or pharmacokinetic parameters from Schedule 1 may suggest that a more frequent dosing schedule is warranted. If Schedule 2 is opened for enrollment, the enrollment on Schedule 1 will be paused. Schedule 2 may stop enrollment earlier (e.g., based on safety) and enrollment in Schedule 1 may be resumed. The

MTD or MAD may be determined for either Schedule 1 or Schedule 2. Alternatively, a less intensive dosing schedule may be instituted if safety, pharmacokinetic and/or pharmacodynamic

The planned dose escalation is in half-log increments as outlined in Table 1.

Table 1: SL-172154 Dose Escalation Plan in Phase 1

data on Schedule 1 support less frequent dosing of SL-172154.

Dose Level	IV Dose of SL-172154 (mg/kg) ^{a,b,c,d}	Duration of Infusion ^e
Level 1 - starting dose	0.1	30 minutes (+/- 10 minutes)
Level 2	0.3	30 minutes (+/- 10 minutes)
Level 3	1.0	30 minutes (+/- 10 minutes)
Level 4	3.0	60 minutes (+/- 15 minutes)
Level 5	10.0	60 minutes (+/- 15 minutes)

- a) Dosing will begin on Schedule 1 with SL-172154 administered in 28-day cycles on days 1, 8, and 15 in cycle 1 and then on days 1 and 15 in cycles \geq 2.
- **b)** Dose escalation on Schedule 2 may be tested. If Schedule 2 is opened, SL-172154 may be administered once weekly on days 1, 8, 15 and 22 of each 28-day cycle.
- c) Intermediate or higher dose levels may be tested based on emerging safety and pharmacodynamic data.
- d) The actual body weight in kilograms (kg) will be used for dose calculation in all subjects whose body weight is ≤100 kg. For subjects with body weight >100 kg, the dose to be administered should be the same as that calculated for a subject weighing 100 kg.
- e) Infusion time may change based on final drug volume needed for administration, safety and tolerability of the infusion for the subject and/or observed safety findings during the study. Protocol Clarification Memo dated on 04MAR2022 clarified that the duration of infusion was to be increased from 60 minutes to 120 minutes (± 20 minutes) for 10 mg/kg dose level. Protocol Clarification Memo dated on 3JUN2022 clarified that the duration of infusion was to be increased from 60 minutes to 120 minutes (± 15 minutes) for 3 mg/kg dose level.

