Categorical variables will be summarized by counts and by percentages of subjects in the corresponding categories. Percentages are routinely based on the total number of the specified population N if not otherwise specified. For frequency counts, categories whose counts are zero will be displayed for the sake of completeness. For example, if none of the subjects discontinue due to "lost to follow-up," this reason will be included in the table with a count of 0. Categories with zero counts will not have zero percentages displayed.

All confidence intervals (CIs) will be constructed at the 95% confidence level, unless specified otherwise.

All analyses and tabulations will be performed using SAS® v9.4 or above.

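### SAP 9.4 reads the Cmax slope on dose alone against 1, although planned infusion time rises with dose and pulls that slope down

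*SAP*

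**What the plan says.** SAP 9.4 applies the power model to AUC0-inf, AUC0-last, AUCtau, Cmax and Ctrough: "A statistical linear relationship between the ln-transformed PK parameters and the ln-transformed actual dose received in mg will be fitted", "using a mixed effect model with ln-transformed dose as a fixed effect and subject as random effect". It adds that a slope of 1 "would correspond to perfect dose proportionality". Dose-normalised parameters are divided by total mg administered and shown as box plots by dose level. The section also says "Additional predictors may be included in the model", without naming any, and that the assessment "will not be based strictly on statistical rule criteria". Infusion duration is not mentioned in the section.

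SAP 3.1, Table 1, gives 30 minutes for 0.1, 0.3 and 1.0 mg/kg and 60 minutes for 3 and 10 mg/kg. Footnote e reports two protocol clarification memos, of 4 March 2022 for 10 mg/kg and 3 June 2022 for 3 mg/kg, each of which "clarified that the duration of infusion was to be increased from 60 minutes to 120 minutes". The SAP carries the date 17 January 2023, so these durations were known when 9.4 was written.

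The only numerical half-lives are from monkeys (Protocol 1.2.4). The mean terminal half-life "on Day 1 was approximately 0.4 hours following a 1 mg/kg dose", and was about 1.1 h at 10 mg/kg and 0.9 h at 40 mg/kg.

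**The concern.** For a constant-rate infusion, the concentration when the infusion stops depends on dose and on how much drug is eliminated or distributed while it runs. If the higher doses run longer, their Cmax per mg is lower even when kinetics are linear. A slope of 1 is then the wrong reference for Cmax across levels with different durations.

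The dose-normalised box plots and by-dose summaries of Cmax share the fault, so they cannot correct the regression. The possible consequence is a wrong statement about Cmax proportionality, in either of two forms. A real more-than-proportional rise could be hidden, or linear kinetics could be reported as less than proportional. Cmax has weight in this programme: the starting dose was derived from a target Cmax on an assumption of dose proportionality (Protocol 3.2), and PK is part of the evidence for the recommended Phase 2 dose.

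**Working it through.** **Inputs.** Doses 0.1, 0.3, 1, 3 and 10 mg/kg and infusion times from SAP Table 1 and footnote e. Half-lives of 0.4 and 1.1 h from Protocol 1.2.4. Human half-life is an assumption. Protocol 4.1 expects 30 days to exceed five half-lives, which implies only that it is below 6 days (144 h).

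**Formula.** One compartment, constant-rate infusion of duration T, sampled at end of infusion:

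Cmax = (Dose/V) × F(T), where F(T) = (1 − exp(−kT))/(kT) and k = ln 2 / half-life.

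I fitted ln Cmax on ln dose by unweighted least squares over the five levels, without noise. The centred log doses are −2.282, −1.183, 0.021, 1.120 and 2.324, with sum of squares 13.26. If the three lower levels share one duration and the two upper levels share another:

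slope = 1 + [(1.120 + 2.324)/13.26] × ln(F_upper/F_lower) = 1 + 0.260 × ln(F_upper/F_lower).

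**The plan's own reference.** With one duration throughout, F_upper/F_lower = 1 and the slope is 1.000 at any half-life. This reproduces the SAP's reference value.

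**Planned durations, half-life 0.4 h.** k = 1.733 per hour, so F is 0.669 at 30 min, 0.475 at 60 min and 0.280 at 120 min.
- 60 v 30 min: ratio 0.710, slope 1 + 0.260 × (−0.342) = 0.911.
- 120 v 30 min: ratio 0.418, slope 1 + 0.260 × (−0.872) = 0.773.

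**Other half-lives.** Slopes are for the stated duration at 3 and at 10 mg/kg, with 30 min below:

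| Half-life (h) | Cmax per mg, 60 v 30 min | Cmax per mg, 120 v 30 min | Slope, 60/60 min | Slope, 60/120 min | Slope, 120/120 min |
|---|---|---|---|---|---|
| 0.4 | 0.710 | 0.418 | 0.911 | 0.818 | 0.773 |
| 1.1 | 0.865 | 0.663 | 0.962 | 0.916 | 0.893 |
| 2 | 0.920 | 0.786 | 0.978 | 0.951 | 0.937 |
| 4 | 0.959 | 0.882 | 0.989 | 0.974 | 0.967 |
| 24 | 0.993 | 0.979 | 0.998 | 0.996 | 0.994 |

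At 144 h every slope is 0.999 or higher.

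**Half-life differing by dose, as in monkeys.** Take 0.4 h up to 1 mg/kg and 1.1 h above, with the same V. F for 1.1 h is 0.858, 0.742 and 0.568 at 30, 60 and 120 min.
- Equal 30 min: ratio 0.858/0.669 = 1.282, slope 1.06.
- 60 min at 3 and 10 mg/kg: ratio 0.742/0.669 = 1.109, slope 1.03.
- 120 min at 3 and 10 mg/kg: ratio 0.568/0.669 = 0.850, slope 0.96.

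**AUC.** AUC0-inf = Dose/CL does not contain T. At a single half-life its slope is 1.000 whatever the durations. In the dose-dependent case AUC is proportional to Dose × half-life, so the ratio is 1.1/0.4 = 2.75 and the slope is 1 + 0.260 × 1.012 = 1.26. AUC would show the departure that Cmax hides.

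**Adding ln(duration).** The Cmax slope returns to 1.000 for 60/60 and 120/120 min, and to 1.003–1.013 for 60/120 min (half-lives 0.4, 1.1 and 4 h). Across the five levels, log dose and log duration correlate at 0.86–0.89. The variance inflation is 3.9–4.6, which multiplies the slope's standard error by about 2.0–2.15. If each upper level were split evenly between 60 and 120 min, the correlation would be 0.79, the inflation 2.7 and the multiplier about 1.6.

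**The case against.** The other side has several good points.

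- **Direction of the harm.** A reader might infer that a slope below 1 will be mistaken for target-mediated kinetics. The documents point the other way. Protocol 3.2 describes rapid clearance through an antigen sink and target-mediated uptake, and saturating a sink gives more than proportional exposure. Monkey mean Cmax was 1,230 ng/mL at 1 mg/kg (GLP study) and 727,000 ng/mL at 40 mg/kg (dose-range-finding study). That is 591-fold for a 40-fold dose, a log slope of about 1.7, though only indicative across two studies. Masking is the likelier error. This stands.
- **Size.** A reader might take 0.77 as the expected slope. It applies a monkey half-life seen at 1 mg/kg to the two highest levels, and the effect is negligible if human half-life is a day or more. This stands.
- **Pooling.** A reader might infer that 60- and 120-minute infusions will be mixed within a level. The documents do not say how many subjects, if any, were treated before each memo. Mixing is possible, not shown.
- **Existing safeguards.** AUC goes through the same model, extra predictors are allowed, SAP 9.2 plots individual profiles with actual infusion times, and SAP 6.7 lists each infusion's duration. A careful reader could spot a Cmax slope below an AUC slope. These help, but none changes the Cmax slope, normalisation or summaries as written, and 9.4 does not say that AUC governs if they disagree.
- **Consequences.** No decision rule uses the Cmax slope, the PK merge follows database lock (SAP 9), and the Phase 2 dose rests on the totality of data. The documents do not support a claim that a wrong dose would follow.

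**Conclusion.** The point holds as a defect of the Cmax part of SAP 9.4. As specified, the slope and the mg-normalised Cmax mix the effect of dose with that of a longer infusion, and the bias is downward. At a single half-life the slope under linear kinetics is 0.77–0.91 at 0.4 h, 0.89–0.96 at 1.1 h, 0.97–0.99 at 4 h and above 0.99 at 24 h. With the monkey half-lives by dose, a slope of 1.06 at equal durations becomes 1.03 or 0.96, enough to cross the reference value.

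These figures assume one compartment, equal weight for the five levels, planned rather than actual durations, and Cmax at end of infusion. Protocol 6.1.1 supports the last, with a sample within 5 minutes of stopping. A long terminal half-life would not by itself remove the concern. In an illustrative two-compartment case with assumed values (80% of the initial concentration in a phase of half-life 0.25 h, the rest at 6 h), the slope is 0.92 to 0.83. AUC0-inf is unaffected under linear kinetics. The analysis is secondary and descriptive, so this is a worthwhile correction to interpretation, not a threat to the trial's primary conclusions.

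**What to change.** In SAP 9.4:

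1. State that the dose-proportionality conclusion rests on AUC, with AUC0-inf preferred where it is reliably estimated.
2. State that the Cmax slope is not to be read against 1 across levels with different infusion times.
3. Show Cmax and dose-normalised Cmax by infusion duration (30, 60, 120 min), splitting 3 and 10 mg/kg wherever both durations were used.
4. Add ln(actual infusion duration) to the Cmax power model as a sensitivity analysis only.

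No new data are needed: Protocol 6.1.1 records infusion start and stop times, and SAP 6.7 already lists duration. The cost is small subgroups, since cohorts are of about three subjects, and in the sensitivity model a slope standard error about 1.6 to 2.15 times larger. That loss of precision is why the covariate model should not be primary. Nothing here implies a change to any infusion time.
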